8.2. Secondary Immunogenicity Analyses

Humoral immune responses in terms of strain-specific IIV4 HAI and Neut antibody titers will be summarized by study arm at each time point. Descriptive summary statistics will be provided for all assays and time points including number of subjects with non-missing results, number and percentage of subjects with titers ≥1:40, number and proportion of subjects achieving seroconversion, and GMTs along with corresponding 95% CIs. Clopper-Pearson exact confidence intervals will be presented for proportion endpoints. Summaries of humoral immunogenicity endpoints are presented in Table 30, Table 31, Table 32, Table 33, Table 34, Table 35, Table 36, and Table 37.

HAI and Neut seroconversion by Day 172 or Day 200, the percentage of subjects with titer ≥40, and GMT's against the 2018-2019 IIV4 vaccine strain on Days 1, 43, 182, and 200 will be summarized as described above.

The reverse cumulative distributions of HAI and Neut assays against each strain will be displayed in Figure 10, Figure 11, Figure 12, Figure 13, Figure 14, Figure 15, Figure 16, and Figure 17. The Spearman correlation between HAI, Neut, and M-001 antibody titers will be calculated at each time point over all groups. The correlation will be depicted in scatter plots beginning at Figure 18 and continuing through Figure 29.

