2.2. Rationale

Seasonal and pandemic influenza pose perpetual threats to human populations. The rapid and constant evolution of influenza viruses likewise poses challenges to the development of vaccines for the prevention and control of influenza. Recent vaccine development efforts have focused on the development of "universal" influenza vaccines; that is, vaccines which could offer protection against multiple influenza subtypes. BiondVax has developed a novel vaccine, M-001, that has been shown in preclinical and clinical trials to stimulate both the humoral and cellular arms of the immune system. When used as a primer ahead of a strain-specific boost, M-001 enhances immunity to strains contained within the boost and to drifted strains. The goals of the study are to determine the safety of a M-001 prime followed by an IIV4 boost vaccine strategy, and to assess the effects of M-001 immunization on cellular and humoral immunity to seasonal influenza virus strains.

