11.5.3. Humoral Immunogenicity Data

Summaries and analysis of immunogenicity data will be presented for the ITT and PP populations; the PP population will be considered the primary analysis.

Immune responses in terms of strain-specific (IIV4 strains) HAI and Neut antibody titers will be summarized by treatment arm at each time point. Analyses at all time points will include proportion of subjects with titers ≥ 40 and geometric mean titers (GMTs). Additionally the proportion of subjects achieving seroconversion from Day 172 to Day 200 (defined as either a pre-vaccination titer < 10 and a post-vaccination titer ≥ 40 or a pre-vaccination titer ≥ 10 and a minimum four-fold rise in post-vaccination antibody titer) will be presented. All summaries will include the corresponding 95% confidence intervals.

The proportion of subjects with seroconversion from Day 172 to 200 will be compared to evaluate the effect of M-001 priming using a two-sided Likelihood Ratio Test.

M-001 antibody response will be summarized by GMTs the proportion of subjects achieving seroconversion (defined as a minimum four-fold rise in post-vaccination ELISA antibody titer) at each time point, with corresponding 95% confidence intervals.

The correlation between HAI, Neut, and M-001 antibody titers will be evaluated. Plots such as reverse cumulative distributions or longitudinal presentations of GMTs will be presented for each assay.

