3.2.2. Secondary Outcome Measures

Safety

- Occurrence of all SAEs, from the time of receiving the first M-001 or placebo study vaccination through the end of the study
- Occurrence of all unsolicited non-serious AEs from the time of first study vaccination through 21 days after each M-001 vaccination

Immunogenicity

- For HAI and Neuts, the percentage of subjects achieving seroconversion (defined as either a prevaccination titer <10 and a post-vaccination titer ≥40 or a pre-vaccination titer ≥10 and a minimum four-fold rise in post-vaccination antibody titer) to IIV4 vaccine viruses from Day 172 to Day 200
- For HAI and Neuts, the percentage of subjects with an antibody titer of 40 or greater and geometric mean titers (GMTs) vs. IIV4 vaccine viruses on Days 1, 43, 172 and 200

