3.3. Study Definitions and Derived Variables

Geometric mean percentages (GMPs) are calculated as the product of the observed percentages raised to the 1/Nth root, where N is the number of observed values.

The baseline value for cellular and humoral immunity will be defined as the value obtained on Day 1 prior to M-001 vaccination.

M-001 antibody response after baseline will be summarized by GMTs and the proportion of subjects achieving seroconversion (defined as a minimum four-fold rise in post-vaccination ELISA antibody titer) at each time point, with corresponding 95% confidence intervals.

For individual subjects, fold rise will be calculated as the ratio of: $\frac{post-vaccination\ titer}{pre-vaccination\ titer}$, where pre-vaccination value is always the result obtained at Day 1, prior to the first M-001 dose.

Seroconversion for HAI and Neut assays is defined as either a pre-vaccination titer < 1:10 and a post-vaccination titer $\ge 1:40$, or a pre-vaccination titer $\ge 1:10$ and a minimum four-fold rise in post-vaccination titer.

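### HAI and Neut GMTs are a secondary outcome, but neither the protocol nor the SAP plans a between-arm GMT ratio; a Day 1-adjusted ratio should be added to SAP 8.2.

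*SAP*

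**What the plan says.** Protocol 2.2 names as a goal to "assess the effects of M-001 immunization on cellular and humoral immunity to seasonal influenza virus strains". SAP 3.2.2, like Protocol 3.2.2, lists two HAI/Neut secondary outcomes. One covers the percentage with titer 40 or more and "geometric mean titers (GMTs) vs. IIV4 vaccine viruses on Days 1, 43, 172 and 200". The other is seroconversion, which includes a "minimum four-fold rise in post-vaccination antibody titer) to IIV4 vaccine viruses from Day 172 to Day 200".

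Protocol 11.5.3 gives GMTs, the proportion at 40 or above and seroconversion by arm, each with a 95% CI. It then states one between-arm antibody analysis: "The proportion of subjects with seroconversion from Day 172 to 200 will be compared to evaluate the effect of M-001 priming", by a two-sided likelihood ratio test.

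SAP 8.2 reads: "Humoral immune responses in terms of strain-specific IIV4 HAI and Neut antibody titers will be summarized by study arm at each time point". It adds reverse cumulative distributions by strain and Spearman correlations between assays. It contains no between-arm test, ratio or difference. The Table 30 shell, which Tables 31 to 37 follow, has one column per arm and nothing else. SAP Section 12 lists two changes from the protocol. Dropping the likelihood ratio test is not one of them.

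The reference day for seroconversion is not consistent. SAP 3.2.2 and Protocol 11.5.3 measure from Day 172. SAP 3.3 defines fold rise as one "where pre-vaccination value is always the result obtained at Day 1, prior to the first M-001 dose". SAP 8.2 speaks of "HAI and Neut seroconversion by Day 172 or Day 200", and Table 30 shows seroconversion at Days 22, 43, 172 and 200, which fits a Day 1 reference.

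**The concern.** A randomised comparison of M-001 with saline before IIV4 is the design's means of showing whether priming improves the antibody response. For a named secondary outcome, a reader would expect the size of that effect and its uncertainty. The plan leaves the reader to compare two separate intervals. Those can overlap when the interval for the ratio excludes 1, so overlap is a poor guide. The SAP does plan between-arm differences with 95% CIs for solicited symptoms (Table 48), so their absence here is not a general convention.

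The Day 1 titer and the stratification factors are collected for every subject but not used in the antibody analysis. At stake is a modest but real gain in titers that could go unquantified, or be estimated less precisely than the data allow.

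**Working it through.** **1. What each document plans between arms for antibody.**

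| Quantity | Protocol 11.5.3 | SAP 8.2, Tables 30-37 |
|---|---|---|
| GMT | per arm with CI | per arm with CI |
| Titer 40 or above | per arm with CI | per arm with CI |
| Seroconversion | per arm, plus likelihood ratio test | per arm with CI |
| GMT ratio, any day | none | none |

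**2. The plan's own power method, reproduced.** Protocol Table 10 concerns T cells: 2-fold, SD 0.50 log10, two-sided t-test, alpha 0.05. SE = 0.50 × √(2/60) = 0.0913, and 0.301/0.0913 = 3.30. The noncentral t gives 90.5% (stated 90). At 54 per arm it gives 87.3% (stated 87). There is no corresponding figure for antibody.

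**3. Inputs for antibody.**
- From the documents: 60 per arm less up to 5% per-protocol exclusion = 57 (Protocol 11.3.3); titers on the grid 10 × 2^k, with values below 10 set to 5 (SAP 4.5.2); alpha 0.05 two-sided, borrowed from the T-cell calculation.
- Assumed: SD of log2 titer 1.25, 1.5 or 2.0; Day 1 to Day 200 correlation 0.6; Day 172 to Day 200 correlation 0.65; true Day 200 ratio 1.5; twofold or fourfold mean rise.

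**4. Precision of the ratio at SD 1.5.** Rounding to the doubling grid adds about 1/12 to the variance.
- Observed SD = √(1.5² + 1/12) = 1.53. SE = 1.53 × √(2/57) = 0.286. Unadjusted 95% CI factor = 2^(1.98 × 0.286) = 1.48.
- Correlation on the grid = 0.6 × 2.25/2.333 = 0.579. Adjusting for Day 1 multiplies the SE by √(1 − 0.579²) = 0.816, giving 0.233. Adjusted factor = 2^(1.98 × 0.233) = 1.38.
- Power for a ratio of 1.5 (0.585 log2): unadjusted 0.585/0.286 = 2.04, about 53%; adjusted 0.585/0.233 = 2.51, about 70%.
- The same steps at SD 1.25 and 2.0 give 67% and 33% unadjusted, and 84% and 47% adjusted.

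**5. Why overlapping per-arm intervals are a poor guide.** At SD 1.5 each arm's half-width is 2.00 × 1.53/√57 = 0.405 log2. Two such intervals stop overlapping only at a ratio of 2^0.81 = 1.75. The interval for the unadjusted ratio already excludes 1 at 1.48.

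**6. Simulated power, 57 per arm, priming acting on the IIV4 response only, over the SD range.**

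| Analysis | Power |
|---|---|
| Seroconversion Day 172 to 200, likelihood ratio test | 32-61% |
| Day 200 GMT, unadjusted t-test | 33-67% |
| Day 200 GMT, Day 1-adjusted | 46-82% |

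The last two rows agree with step 4 to within 2 points. The seroconversion row moves by several points with the assumed starting titer and mean rise.

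A separate set of runs used 60 per arm, 1.5- and 2-fold effects and other SDs. The adjusted ratio gained about 6 to 18 points over the seroconversion test. The unadjusted comparison differed from that test by −2 to +3 points.

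**7. A gain already present at Day 172.** Suppose M-001 raises log2 titer by g at both Day 172 and Day 200. The Day 172-based rise is (T200 + g) − (T172 + g) = T200 − T172. This is the same as under placebo, apart from effects near the detection limit. Simulated power for a 1.5-fold gain is about 6-7%, close to alpha. Measured from Day 1, the rise is shifted by g, and the seroconversion test has 27-58%.

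**The case against.** The secondary objective is to assess antibody responses. The formal hypothesis and power calculation concern T cells, and even those comparisons are declared non-confirmatory. A descriptive secondary analysis is a defensible Phase II choice. Per-arm GMTs with intervals, the proportion at 40 or above, reverse cumulative curves and subject listings are all planned. From two independent arms' GMTs and intervals, a reader can reconstruct an approximate unadjusted ratio and CI. All of that stands. It means the data will be visible. It does not supply a prespecified, adjusted estimate.

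Three stronger readings are tempting, and the documents do not support them.
- A reader might infer that the fourfold-rise cut wastes most of the titer information. It does not: an unadjusted GMT comparison does little better than the Day 172-based seroconversion test. The gain comes mainly from Day 1 adjustment.
- A reader might infer that priming is judged only by a dichotomised rise. That describes the protocol's one test ("will be compared to evaluate the effect of M-001 priming using a two-sided Likelihood Ratio Test"). SAP 8.2 plans no between-arm antibody comparison at all.
- A reader might infer that gains present by Day 172 will be missed. That holds for seroconversion measured from Day 172. It does not hold under the Day 1 reference in SAP 3.3, and per-arm GMTs at Days 172 and 200 would show such a gain descriptively.

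**Conclusion.** The point holds as a gap in estimation. A named secondary outcome that serves a stated goal has no planned between-arm estimate in either document. A Day 1-adjusted GMT ratio would narrow the 95% CI factor from about 1.48 to 1.38 at SD 1.5. For a true ratio of 1.5 it would raise power to about 46-82%, against 33-67% unadjusted and 32-61% for Day 172-based seroconversion.

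The blind spot for gains already present at Day 172 (about 6-7% power) is conditional on which reference day governs, and the documents conflict on that.

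That no ratio is planned is certain from the text. The sizes are not: every titer SD, correlation and effect is assumed, because the documents give none. The ordering that puts the adjusted analysis first held throughout the range examined when priming acts on the IIV4 response. This is worth correcting in the SAP, but it does not threaten the trial's primary conclusions.

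**What to change.** In SAP 8.2 and Tables 30 to 37 add, for each strain and assay, the Day 200 GMT ratio (M-001/placebo) with 95% CI. Take it from a linear model of log2 titer on arm, log2 Day 1 titer and the randomisation strata: prior 2017-18 vaccination, and site, which SAP 4.4.3 lists although Protocol 5.4.1 does not. Give the same ratio at Days 43 and 172 so that any gain before IIV4 is visible. Do not adjust for the Day 172 titer: it is measured after randomised treatment, and adjusting for it would remove part of the effect of interest.

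Reconcile the seroconversion reference day across Protocol 11.5.3, SAP 3.2.2, SAP 3.3, SAP 8.2 and Table 30. Either reinstate the protocol's likelihood ratio test or list its removal in SAP Section 12.

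Cost: SAP wording and a contrast column in eight tables, with no new data. The downside is 24 further estimates (4 strains × 2 assays × 3 days) without multiplicity adjustment. They should be labelled non-confirmatory, consistent with the plan's stance on its primary comparisons.

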3.2.2. Secondary Outcome Measures

Safety

- Occurrence of all SAEs, from the time of receiving the first M-001 or placebo study vaccination through the end of the study
- Occurrence of all unsolicited non-serious AEs from the time of first study vaccination through 21 days after each M-001 vaccination

Immunogenicity

- For HAI and Neuts, the percentage of subjects achieving seroconversion (defined as either a pre-vaccination titer <10 and a post-vaccination titer \geq 40 or a pre-vaccination titer \geq 10 and a minimum four-fold rise in post-vaccination antibody titer) to IIV4 vaccine viruses from Day 172 to Day 200
- For HAI and Neuts, the percentage of subjects with an antibody titer of 40 or greater and GMTs vs. IIV4 vaccine viruses on Days 1, 43, 172 and 200

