3.2.3. Exploratory Outcome Measures

- Percentage of subjects achieving seroconversion (defined as a minimum four-fold rise in post-vaccination ELISA antibody titer) and GMTs of ELISA antibody vs. M-001 from Day 1 to Days 22, 43, 78, 172 and 200
- Geometric Mean Percentage of T cell subsets expressing perforin, CD107a, IFN- γ , TNF- α , and IL2, alone or in combination, in CD4 and CD8 cells after stimulation with M-001 peptides at baseline (Day 1) and approximately 14 days after one dose of M-001, 21 and 56 days following the second dose of M-001, and immediately prior to and 14 and 28 days after IIV4
- Percentage of T cell subsets expressing perforin, CD107a, IFN- γ , TNF- α , and IL2, alone or in combination, in CD4 and CD8 cells after stimulation with other influenza A antigens (including seasonal and pandemic influenza antigens) at baseline (Day 1), approximately 14 days after each study vaccination, 21 and 56 days following the second study vaccination and immediately prior to and approximately 14 and 28 days after IIV4
- Percentage of influenza-specific T cell memory subsets expressing discrete memory markers (CCR7, CD45RO, and CD57) at baseline (Day 1) and on study days 15, 36, 43, 78, 172, 186 and 200
- Percentage of influenza-specific CD4+ cell subsets expressing IL-4 or IL-17, T follicular helper cells (CD4+, CXCR5+, PD-1+, IL-21+), T follicular regulatory (Tfr) cells (CXCR5+, PD-1+, CD25+, CD1217+), and Tregs (CD25+, Foxp3+) at baseline (Day 1) and on study days 15, 36, 43, 78, 172, 186 and 200

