11.3.4. Sample Size

This study is planned to enroll 120 subjects (60 per treatment arm). The following illustrates the precision and power that is available for select estimates and comparisons of interest.

[Table 8](#) indicates the probability of observing one or more safety events, such as solicited injection site or systemic reactogenicity events or an unsolicited non-serious AE of a particular type, for a single treatment arm (N=60) and all enrolled subjects (N=120).

Table 8: Power (%) to Detect Safety Events

Event Frequency	Single Treatment Arm N=60	Two Treatment Arms N=120
≥10% Very Common	99.8	>99.9
≥1% Common	45.3	70.1
≥0.1% Uncommon	5.8	11.3
≥0.01% Rare	<1	1.2

Binomial confidence intervals (CI) are widest (have the least precision) when the response rate is 50%. [Table 9](#) is presented to indicate the worst case scenario for precision of observed exact (Clopper-Pearson) binomial confidence intervals.

Table 9: Precision of Binomial Confidence Intervals:

	N	95% CI
Single Treatment Arm	60	(36.8,63.2)
Two Treatment Arms	120	(40.7, 59.3)

With N = 60 subjects per arm and assuming the standard deviation of logGMP is 0.75, the study will have 80% power to detect a 2.5-fold increase in the GMP of T cell subsets expressing IFN- γ . [Table 10](#) illustrates a power analysis considering a range of standard deviations for log GMP and a range of GMP fold-change with N=60 subjects per arm, and further includes the power under the conservative assumption of 10% drop out in each treatment arm. Power is calculated for a two-sided t-test with significance level (alpha) 0.05 using PROC POWER in SAS 9.4.

While there will be multiple comparisons performed for this primary immunogenicity objective (for each of five parameters alone measured in CD4 and CD8 T cells plus any combinations measured), it is assumed that these analyses are not intended to be confirmatory and thus no adjustment for multiple comparisons is considered.

Table 10: Power Analysis for Primary Immunogenicity Endpoint

GMP _e /GMT _c {fold- change}	$\log_{10}(\text{GMP}_M) - \log_{10}(\text{GMP}_c)$ {log-difference}	Std Dev \log_{10} (GMP)	Power (N = 60)	Power (N=54) 10% drop out
1.5	0.18	0.25	97	96
		0.50	49	45
		0.75	26	23
2	0.30	0.25	>99	>99
		0.50	90	87
		0.75	58	54
3	0.48	0.25	>99	>99
		0.50	>99	99
		0.75	93	90
4	0.60	0.25	>99	>99
		0.50	>99	>99
		0.75	99	98

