4. INVESTIGATIONAL PLAN

4.1. Overall Study Design and Plan

DMID 14-0112 is a Phase II randomized, double-blind, placebo-controlled trial in a sample of 120 males and non-pregnant females, 18 to 49 years old, inclusive, who are in good health and meet all eligibility criteria. This clinical trial is designed to assess the safety, reactogenicity, and immunogenicity of two priming doses of M-001 followed by administration of IIV4.

Subjects are assigned randomly to 1 of 2 study arms (60 subjects per study arm) to receive two doses of the M-001 vaccine or placebo followed by a single dose of IIV4 (see Table 1).

- Group A receives two 1 mg doses of M-001, on Days 1 and 22 followed by a single dose of IIV4 on approximately Day 172 (±30).
- Group B receives saline placebo on both Days 1 and 22, followed by a single dose of IIV4 approximately on Day 172 (±30).

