- Figure 12: Reverse Cumulative Distribution of Hemagglutination Inhibition Antibody Against B/Colorado/6/2017 (B Victoria Lineage) by Study Day and Study Arm, Per Protocol Population
- Figure 13: Reverse Cumulative Distribution of Hemagglutination Inhibition Antibody Against B/Phuket/3073/2013 (B Yamagata Lineage) by Study Day and Study Arm, Per Protocol Population
- Figure 14: Reverse Cumulative Distribution of Neutralizing Antibody Against A/Michigan/45/2015 X-275 (H1N1) by Study Day and Study Arm, Per Protocol Population
- Figure 15: Reverse Cumulative Distribution of Neutralizing Antibody Against A/Singapore/INFIMH-16-0019/2016 NIB-104(H3N2) by Study Day and Study Arm, Per Protocol Population
- Figure 16: Reverse Cumulative Distribution of Neutralizing Antibody Against B/Colorado/6/2017 (B Victoria Lineage) by Study Day and Study Arm, Per Protocol Population
- Figure 17: Reverse Cumulative Distribution of Neutralizing Antibody Against B/Phuket/3073/2013 (B Yamagata Lineage) by Study Day and Study Arm, Per Protocol Population

Figure 18: Correlation of Hemagglutination Inhibition Antibody and Neutralizing Antibody Against A/H1N1 by Study Day and Study Arm, Per Protocol Population

[Implementation Note: A generic sample figure is shown below. The scatter plots should be presented in a single figure with separate panels for each visit. Visit labels should be included in the panel header. Within each panel distinct marker types and colors should be used to indicate the 2 vaccination groups, with vaccination group labels included in a legend. The spearman correlation should be calculated over all subjects and annotated within each panel header after the visit label as "r=0.xx, p=0.xx". The x-axis should be labeled by "Hemagglutination Inhibition Antibody (Titer)" and the y-axis by "Neutralizing Antibody (Titer)".]

[figure not shown]

Figures with similar format:

- Figure 19: Correlation of Hemagglutination Inhibition Antibody and M-001 Antibody Against A/H1N1 by Study Day and Study Arm, Per Protocol Population
- Figure 20: Correlation of Neutralizing Antibody and M-001 Antibody Against A/H1N1 by Study Day and Study Arm, Per Protocol Population
- Figure 21: Correlation of Hemagglutination Inhibition Antibody and Neutralizing Antibody against A/H3N2 by Study Day and Study Arm, Per Protocol Population
- Figure 22: Correlation of Hemagglutination Inhibition Antibody and M-001 Antibody Against A/H3N2 by Study Day and Study Arm, Per Protocol Population

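### Pooled Spearman correlations between M-001 antibody and HAI or Neut mix between-arm with within-arm association; a per-arm or arm-stratified coefficient should be printed

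*SAP*

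**What the plan says.** Protocol 11.5.3 leaves the method open: "The correlation between HAI, Neut, and M-001 antibody titers will be evaluated". The choice to pool is made in SAP 8.2: "The Spearman correlation between HAI, Neut, and M-001 antibody titers will be calculated at each time point over all groups". The implementation note for Figure 18 (SAP Appendix 2, under 14.2.2) repeats it: "The spearman correlation should be calculated over all subjects and annotated within each panel header after the visit label". Each panel header thus carries one r and one p. Figures 19 to 29 are listed as following the same format. The arms are separated only visually: "Within each panel distinct marker types and colors should be used to indicate the 2 vaccination groups". Neither document plans a within-arm, stratified or partial coefficient.

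On exposure, SAP 4.1 says "Group B receives saline placebo on both Days 1 and 22", so the control arm receives no M-001 at any visit.

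On timing, Protocol 3.2.2 sets for HAI and Neut "the percentage of subjects with an antibody titer of 40 or greater and GMTs vs. IIV4 vaccine viruses on Days 1, 43, 172 and 200", and Protocol 3.2.3 sets for the ELISA "GMTs of ELISA antibody vs. M-001 from Day 1 to Days 22, 43, 78, 172 and 200". The visits shared by all three assays are Days 1, 43, 172 and 200.

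**The concern.** A reader who sees r and p above a scatter plot will take them to say whether subjects with more M-001 antibody also have more HAI or Neut antibody. When one variable is driven by randomised arm, a coefficient over both arms does not isolate that. It combines the association among subjects of the same arm with the product of the two arm differences. The arm differences are already reported by arm in SAP Tables 30 to 37 and 44, so the part of the correlation that would add information is the within-arm part. Colouring the points by arm helps the eye but does not change the printed numbers.

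The scope is limited. Figures 18, 21, 24 and 27 plot HAI against Neut and do not involve M-001 antibody. At Day 1 the arms differ only by chance. That leaves 8 figures × 3 visits (Days 43, 172, 200) = 24 printed r and p pairs.

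**Working it through.** The plan gives no figure for this analysis, so there is none to reproduce. The check asks what a pooled coefficient shows under stated conditions.

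**Inputs from the documents.** There are 60 subjects per arm (Protocol 11.3.4). Immune responses are analysed in the per-protocol population (SAP 8), with up to 5% excluded (Protocol 11.3.3): 60 × 0.95 = 57 per arm.

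**Assumed inputs, because the documents give none.** The arm shift in log M-001 antibody is dM = 1 to 3 SD. The arm shift in log HAI or Neut is dH = −0.5, 0, 0.5 or 0.8 SD. The within-arm correlation is ρ = 0 or 0.3, and the two-sided level is 0.05. The p-value thresholds in SAP 5 concern arm differences and do not cover correlations.

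**Formula.** For two equal arms with unit within-arm SD, pooling adds dM·dH/4 to the covariance and d²/4 to each variance, so on the Pearson scale

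r_pooled = (ρ + dM·dH/4) / √[(1 + dM²/4)(1 + dH²/4)].

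The cases follow directly:

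- ρ = 0, dH = 0: the numerator is 0 whatever dM is, so r_pooled = 0.
- ρ = 0.3, dH = 0: 0.3/√2 = 0.21 at dM = 2; 0.3/√3.25 = 0.17 at dM = 3. The association is diluted.
- ρ = 0, dH = 0.5: 0.25/√(2 × 1.0625) = 0.17 at dM = 2; 0.375/√(3.25 × 1.0625) = 0.20 at dM = 3. An association appears.
- ρ = 0.3, dH = −0.5: (0.3 − 0.25)/1.458 = 0.03 at dM = 2; (0.3 − 0.375)/1.858 = −0.04 at dM = 3. The association is cancelled, then reversed in sign.

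**Simulation of the Spearman coefficient.** Settings: 60 per arm, 2,000 trials per row, bivariate normal log titers. The stratified coefficient is the mean of the two per-arm Fisher z values, transformed back.

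| ρ | dM | dH | Pooled r | Pooled p<0.05 | Stratified r | Stratified p<0.05 |
|---|---|---|---|---|---|---|
| 0 | 2 | 0 | 0.00 | 5.8% | 0.00 | 4.9% |
| 0 | 3 | 0 | 0.00 | 4.5% | 0.00 | 3.8% |
| 0.3 | 0 | 0 | 0.29 | 89.8% | 0.29 | 87.3% |
| 0.3 | 1 | 0 | 0.26 | 80.5% | 0.29 | 88.6% |
| 0.3 | 2 | 0 | 0.19 | 55.6% | 0.28 | 87.0% |
| 0.3 | 3 | 0 | 0.16 | 39.4% | 0.29 | 86.8% |
| 0 | 2 | 0.5 | 0.17 | 48.9% | 0.00 | 4.8% |
| 0 | 3 | 0.5 | 0.20 | 60.1% | 0.00 | 4.9% |
| 0 | 2 | 0.8 | 0.27 | 85.1% | 0.00 | 5.0% |
| 0.3 | 2 | −0.5 | 0.02 | 4.9% | 0.29 | 87.8% |
| 0.3 | 3 | −0.5 | −0.05 | 8.2% | 0.29 | 88.0% |

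Rounding HAI or Neut to a two-fold titer grid, in five selected scenarios, gave much the same results.

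At 57 per arm the pattern is the same. With ρ = 0.3 (Spearman about 0.28), dM = 2 to 3 and dH = 0, pooled r is 0.16 to 0.19 and pooled power 41 to 56%, against about 85% for the stratified coefficient. With ρ = 0, dM = 2 to 3 and dH = 0.5, pooled p<0.05 occurs in about 46 to 58% of trials.

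**The case against.** A reader might infer that the arm difference in M-001 antibody alone can produce a spurious correlation. It cannot. With no HAI or Neut difference and no within-arm relation, pooled r stays at zero and p<0.05 occurs about 5% of the time, however large the M-001 shift. Creating an association needs an arm shift in HAI or Neut as well. The documents support such a shift only at Day 200: Protocol 2.2 describes priming as enhancing immunity to the boost strains, and Protocol 2.1.2 reports higher HAI in an earlier trial, after a three-dose prime before a trivalent vaccine and with no magnitude. At Days 43 and 172 no IIV4 has been given, so the supported effect there is dilution only.

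The other side also has a fair point about the estimand. No objective or outcome measure names this correlation, and neither document says that the within-arm association is the target. If M-001 raises both titers, they are truly associated in the pooled sample, and calling that a false positive presumes the within-arm question. This stands as a reason to label the pooled value rather than call it wrong. It is no reason to print it alone, since the reader cannot tell which component it reflects.

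It also stands that little depends on the result. Figures 18 to 29 carry no topline asterisk, no hypothesis or decision uses the correlation, the plots mark the arms, and Listings 8 to 16 give individual titers with study arm.

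**Conclusion.** The point holds in limited form. For the eight M-001 figures at Days 43, 172 and 200, the single pooled r and p do not separate between-arm from within-arm association. The expected M-001 difference weakens any within-arm association. It can create or reverse one only together with an arm difference in HAI or Neut, plausible at Day 200.

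The direction of these effects follows from the formula. Their size depends entirely on the assumed shifts: at 1 SD in M-001 antibody the dilution is slight (0.29 to 0.26), and at 2 to 3 SD it is substantial. Normal log titers and equal within-arm correlation in the two arms are further assumptions.

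Severity is low. No primary or secondary endpoint conclusion is affected, and a reader should not infer that the HAI–Neut figures or the Day 1 panels share the problem.

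**What to change.** In SAP 8.2 and in the implementation notes for Figures 19, 20, 22, 23, 25, 26, 28 and 29:

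- report Spearman r within each arm at each visit;
- print one arm-stratified coefficient as the panel summary (for example, the back-transformed mean of the two Fisher z values), with its p-value if one is wanted;
- if a pooled r is kept, label it as including the between-arm difference. It need not be dropped.

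Figures 18, 21, 24 and 27 can stay as they are.

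The cost is a few lines of code and no new data. Per-arm estimates are less precise, with about 57 subjects each. The stratified coefficient uses all subjects and, in the 60-per-arm simulations, held false positives at 3.6 to 5.4% and power at 86 to 89% (within-arm ρ of 0.3), whatever the arm shifts.
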